8.5.2 Assessments pre and post hospital discharge

In the case that a participant is discharged from hospital during the study, the following guidelines must be followed:

- If the participant is discharge prior to Day 10, assessments for Day 10/early discharge visit should be completed prior to discharge
- If the participant continues treatment up to Day 10 at home, guidelines in [Section 6.1.3](#) should be followed. The site must contact the participant to assess compliance, and report any dose interruptions and stop dates of treatment, adverse events and relevant concomitant medications in the CRF
- Day 15 and Day 40 visits may be performed via phone call, an onsite visit is not mandated, at a minimum COVID-19 participant status, adverse events and relevant concomitant medications, and study completion status (as applicable) must be assessed.
- In the case that the participant is still hospitalized for either or both Day 15 and Day 40 visits additional assessments requested in [Table 8-1](#) if assessed, as per local practices, may be reported in the relevant CRF pages.

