12.5 Analysis of secondary estimands

Viral clearance at Day 15

The secondary efficacy endpoint of the percentage of participants with negative or below LLOQ - SARS-COV-2 based on PCR by Day 15 will be determined based on the PCR test that is performed at Day 6, Day 10, and Day 15/Day of discharge. Data available in the literature would indicate that when viral clearance is achieved, that participants will not reverse their viral clearance during the 15-day period. The endpoint will be evaluated in the FAS using a logistic regression model with treatment group and whether or not supplemental oxygen is required at randomization as explanatory variables. Odds ratios will be computed for each of active treatment comparisons to placebo. Based on what data is available from the evolving COVID-19 literature, it is anticipated that hydroxychloroquine plus azithromycin will have a greater viral response than hydroxychloroquine and thus will be tested first for the secondary endpoints in the closed testing procedure to preserve familywise Type I error rate at 0.05 two-sided.

The hypotheses in the closed testing procedure will be evaluated in the following order:

H₁: hydroxychloroquine plus azithromycin is not different to placebo with respect to the percentage of participants achieving clinical response by Day 15

H₂: hydroxychloroquine is not different to placebo with respect to percentage of participants achieving clinical response by Day 15

H₃: hydroxychloroquine plus azithromycin is not different to placebo with respect to the percentage of participants achieving viral clearance by Day 15

H₄: hydroxychloroquine is not different to placebo with respect to the percentage of participants achieving viral clearance by Day 15

Time to SARS-CoV-2 negativity/ Time to return to pre-morbid oxygen requirement /Time to discharge (or ready for discharge)

The event rates for these different endpoints will be estimated with Kaplan-Meier product-limit formula. Greenwood's formula will be used to estimate the variance of failure rates and to derive 95% Z-test based confidence intervals for the difference in event rates between active treatment groups and placebo.

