2.6 Analysis of the secondary objectives controlled for multiplicity

2.6.1 Secondary endpoint controlled for multiplicity

The secondary efficacy endpoint of the percentage of participants with negative or below LLOQ - SARS-COV-2 based on PCR by Day 10 will determined based on the PCR test that is performed at Day 6 and Day 10/Day of discharge. Data available in the literature would indicate that when viral clearance is achieved, participants will not reverse their viral clearance during the 15-day period.

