2.6.3 Handling of missing values/censoring/discontinuations

Viral clearance will be based on available PCR results by Day 10, which means that the last available PCR results available at Day 10 or an earlier visit will be used to determine viral clearance status. Patients who do not have PCR results post first dose of treatment will be considered as not having reached viral clearance.

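### Participants discharged before Day 10 with a positive last swab are scored as not cleared by Day 10, although no later swab is required; this understates clearance, more so in an arm discharged sooner

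*SAP*

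**What the plan says.** The schedule in protocol Table 8-1 has post-dose swabs at Day 6 and at Day 10/early discharge. It has none at Day 15 or Day 40, and unscheduled assessments are optional. Protocol section 8.5.2 adds: "If the participant is discharge prior to Day 10, assessments for Day 10/early discharge visit should be completed prior to discharge". For those who continue treatment at home, "The site must contact the participant to assess compliance, and report any dose interruptions and stop dates of treatment, adverse events and relevant concomitant medications"; a swab is not on that list. Later, "Day 15 and Day 40 visits may be performed via phone call, an onsite visit is not mandated", and PCR is not in the minimum set for those contacts.

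SAP section 2.6.1 has clearance by Day 10 "determined based on the PCR test that is performed at Day 6 and Day 10/Day of discharge", and states that a participant who has cleared will not revert within the 15-day period. SAP section 2.6.3 then fixes the status: "the last available PCR results available at Day 10 or an earlier visit will be used to determine viral clearance status". It adds: "Patients who do not have PCR results post first dose of treatment will be considered as not having reached viral clearance". The heading of 2.6.3 names censoring, but the text contains no censoring rule. SAP section 2.6.2 also reports clearance by Day 6, with no separate rule for it.

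Protocol section 12.5 defines the endpoint by Day 15 and plans a test: "The endpoint will be evaluated in the FAS using a logistic regression model". The SAP was cut down after the halt on 19 June 2020 with 20 randomized. It reports counts and percentages only, and its section 5.4 implements no models.

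**The concern.** A positive swab at an early discharge says nothing about the days between discharge and Day 10, yet the rule records those days as a failure to clear. Length of swab follow-up is set by discharge, which is part of the primary clinical response that treatment is meant to change. Readiness for discharge rests on temperature, respiratory rate and oxygen saturation (protocol section 8.3.1), not on a negative PCR, so positive discharges are possible. Participants may also continue study drug at home to Day 10 (protocol section 6.1.3) while any clearance in that time is scored as nil.

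At stake is how the clearance percentages by arm are read. An arm that shortens hospital stay has more unobserved time scored as failure, so a clinical benefit can hide part of an antiviral effect or create a small apparent deficit where none exists.

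**Working it through.** **The plan's own figure.** Protocol section 12.8.2 assumes 80% v 50% by Day 15 with 148 per group and states more than 99% power. By the pooled normal approximation, z = (0.30·√148 − 1.96·√(2·0.65·0.35)) / √(0.80·0.20 + 0.50·0.50) = (3.650 − 1.322)/0.640 = 3.64, so power is 99.99%. The odds ratio is (0.8/0.2)/(0.5/0.5) = 4.0. Both agree with the protocol.

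**Direction.** If clearance does not reverse, carrying a negative result forward is harmless. Only a carried-forward positive can be wrong, and always toward failure. In each arm:

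bias = −(share discharged early and still positive) × (probability of clearing between the discharge swab and Day 10).

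**Size.** The documents give neither factor, so the following are assumptions: exponential clearance from Day 1; true Day 10 clearance P of 50%, 65% or 80%; discharge swab on day d = 4, 6 or 8; share f discharged early 50% (active) v 30% (placebo); discharge independent of clearance.

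- Cleared by the discharge swab: P(d) = 1 − (1 − P)^((d−1)/9)
- Observed clearance: (1 − f)·P + f·P(d) = P − f·(P − P(d))
- Artefact with equal true clearance: −(0.50 − 0.30)·(P − P(d))

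Example, P = 65%, d = 6: P(d) = 1 − 0.35^(5/9) = 44.2%, and the artefact is −0.20 × 20.8 = −4.2 points (observed 54.6% v 58.8%).

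| Discharge swab | P − P(d), for P = 50 / 65 / 80% | Artefact (points) | Chance of falsely significantly worse, 148 per arm (nominal 2.5%) |
|---|---|---|---|
| Day 4 | 29.4 / 35.5 / 38.5 | −5.9 / −7.1 / −7.7 | 17.8 / 22.9 / 28.2% |
| Day 6 | 18.0 / 20.8 / 20.9 | −3.6 / −4.2 / −4.2 | 9.1 / 10.8 / 12.2% |
| Day 8 | 8.3 / 9.2 / 8.6 | −1.7 / −1.8 / −1.7 | 4.7 / 5.1 / 5.4% |

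With equal early discharge (30% v 30%) and equal clearance, the artefact is 0. With 60% v 20% it is −3.3 to −15.4 points. Swabbing everyone at Day 10 regardless of discharge would make it 0.

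**Independence.** In simulations with discharge and clearance correlated (latent correlation 0 to 0.9, median discharge Day 8 v Day 11, equal true clearance) the artefact stayed negative throughout: −5.3 to −6.7 points at correlation 0, and −2.5 to −10.6 at 0.9.

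**With a true effect.** Take 80% v 50% as Day 10 values (an assumption, since the protocol states them for Day 15) and 50% v 30% early discharge. The observed difference is 28.2 points (Day 8), 25.0 (Day 6) or 19.6 (Day 4), with power 99.9%, 99.3% or 92.4% at 148 per arm. The active arm still leads clearly. With a true 65% v 50%, 60% v 20% leaving early and a Day 4 swab, the observed rates are 43.7% v 44.1%, so there the artefact just exceeds the benefit.

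**As enrolled.** One of the 20 was mis-randomized, leaving about 19/3 = 6.33 per arm. Expected extra misclassification for P = 65% and d = 6 is 6.33 × 0.20 × 0.208 = 0.26 participant. But one such participant moves a rate by 1/6, about 17 points.

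**The case against.** The strongest reply is that no planned comparison is affected. The carry-forward rule appears only in the SAP, which is descriptive. The 148-per-arm logistic test is in the protocol, which uses Day 15 and has no last-result rule. Error rates and power that join the two describe an analysis neither document plans. This stands: such figures show what the rule would do at full size and nothing about the halted study.

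A reader might infer that an arm discharged sooner will look worse than placebo. The documents do not support that; it holds only if the artefact exceeds any antiviral benefit. A reader might also infer that positive discharges will be common. Neither document gives a figure; they show only that a negative PCR is not a discharge condition. Optional unscheduled swabs could also count, since SAP section 2.1.1.7 does not rely on nominal visits for clearance. Nor is a false win for an arm that delays discharge a likely confirmatory result: protocol section 12.5 tests clinical response (H1, H2) before clearance (H3, H4), and that response is built on discharge.

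The protocol also plans Kaplan-Meier estimates of time to SARS-CoV-2 negativity, which can accommodate unequal swab follow-up. That is fair to the protocol, but the SAP keeps the endpoint in Table 1-1 and gives it no analysis in section 2.7, so nothing in the current SAP offsets the rule.

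Finally, censoring is not a full cure. In simulations with equal true clearance (50% by Day 15) and assumed lognormal discharge (medians 6 v 10 days, sigma 0.5), the arm difference under the SAP rule v an interval-censored (Turnbull) estimate was −7.6 v −4.7 points at latent correlation 0.3, −9.1 v −7.8 at 0.6, and −6.2 v +6.0 at −0.3. Censoring removed the bias only at correlation 0. This stands, and limits censoring to a sensitivity analysis.

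**Conclusion.** The concern holds as a defect in the scoring rule with a known direction and an uncertain size. SAP section 2.6.3 counts an early positive discharge as not cleared by Day 10. By the same logic, anyone discharged positive before Day 6 counts as not cleared by Day 6. Clearance is understated in every arm with such participants, and more in an arm discharged sooner.

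With no true difference and 50% v 30% discharged early, the artefact is about 2 to 8 points, depending on assumed discharge day and clearance rate. It vanishes if nobody leaves positive. These figures rest on the no-reversal assumption and on the distributions stated above, none of which the documents supply. For the study as halted, the consequence is one of reporting: with about six per arm, a participant whose Day 10 status is unknown would be shown as a virologic failure.

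**What to change.** In SAP section 2.6.3, stop counting a live discharge before Day 10 with a positive last swab as an observed failure. Keep the FAS denominator and report for each arm:

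- cleared by Day 10;
- observed not cleared at Day 10, with deaths counted as failures as in protocol section 2.2;
- discharged PCR-positive, Day 10 status unknown (unless an unscheduled swab by Day 10 settles it);
- day of last swab;
- two bounds on the clearance rate, with the unknowns counted as all not cleared and as all cleared. The lower bound keeps the present treatment of these participants, so the planned summary is not lost.

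Do the same for Day 6.

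Do not use the number swabbed at each day as denominator. That conditions on still being in hospital, a post-randomization outcome; in the lognormal simulations it gave differences of −7.2, −11.5 and +9.3 points (correlations 0.3, 0.6, −0.3) where the truth was 0.

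For a full-size analysis under protocol section 12.5, add an interval-censored estimate beside the stated rule as a sensitivity analysis, censoring these participants at their last swab and keeping death as failure. State that it assumes discharge is uninformative about later clearance, and that it removes the bias only partly if the two are positively correlated.

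The cost is SAP wording, light programming, and results that are wider or given as bounds. No new swabs are needed.

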2.7 Analysis of other secondary efficacy objective(s)

2.7.1 Other secondary endpoints

Time to return to pre-morbid oxygen requirement

The number (percentage) of participants who returned to pre-morbid oxygen requirement by Day 15 and by Day 28 will be summarized. Return to pre-morbid oxygen requirement is defined as no need of mechanical ventilation in any participants and no need of supplemental oxygen in any participants without pre-morbid oxygen requirement. Analysis will be performed on the FAS.

Time to discharge (or ready for discharge)

The number (percentage) of participants ready to be discharged by Day 15 and by Day 28 will be summarized. Analysis will be performed on the FAS.

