1.2 Purpose

This clinical trial is designed to evaluate the efficacy and safety of HCQ and HCQ in combination with azithromycin compared to a placebo in adult participants hospitalized with moderate to severe COVID-19 disease.

Patients with moderate COVID-19 disease are considered to be those with peripheral capillary oxygen saturation (SpO₂) > 94% on room air and requiring hospitalization; patients with severe COVID-19 disease are those requiring hospitalization with peripheral capillary oxygen saturation (SpO₂) ≤ 94% on room air, or the need for oxygen supplementation; respiratory rate >24 breaths per min; heart rate >100 beats per min; systolic blood pressure <90 mm Hg). However, in this study, participants critically ill who require mechanical ventilation or admission to an intensive care unit prior to the initiation of study treatment are excluded.

This study is being conducted to determine whether oral hydroxychloroquine can safely and effectively be used to mitigate, treat, or cure COVID-19 or limit the harm of the COVID-19 pandemic in accordance with the Secretary of the Department of Health and Human Services' (HHS's) Declaration under the Public Readiness and Emergency Preparedness Act for medical countermeasures against COVID-19 (COVID-19 Declaration) effective February 4, 2020. In addition, the purpose of this study is to test whether oral hydroxychloroquine drug product, either as a monotherapy or in combination with azithromycin, results in clinical benefit in patients hospitalized with COVID-19. This study is authorized to proceed under an approved investigational new drug application (IND) in accordance with the public health and medical response of FDA, an Authority Having Jurisdiction as described under the PREP Act, to prescribe, administer, deliver, distribute or dispense this Covered Countermeasure as defined by and following the HHS's COVID-19 Declaration.

2 Objectives and endpoints

Table 2-1 Objectives and related endpoints

Objectives	Endpoints

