5.2 Exclusion criteria

Participants meeting any of the following criteria are not eligible for inclusion in this study.

1. Use of other investigational drugs within 5 half-lives or 30 days of enrollment whichever is longer
2. Participation in any other clinical trial of an experimental treatment for COVID-19 within 5 half-lives or 30 days of enrollment whichever is longer
3. Expectation of concurrent treatment with other agents with actual or potential direct acting antiviral activity against SARS-CoV-2 during study drug dosing period, including but not limited to oseltamivir and protease inhibitors
4. History of hypersensitivity to any of the study treatments or its excipients or to drugs of similar chemical classes.

5. Requires, in the judgement of the investigator, admission to the intensive care unit (ICU) or mechanical ventilatory support (invasive or non-invasive) prior to the initiation of study drug
(There might be a participant who cannot be admitted to the ICU, even if the participant's condition is severe enough, due to administrative reasons under the current circumstances. This case is also considered under admission to the ICU judged by the investigator)
6. Evidence of cytokine storm syndrome or multi-organ system failure
7. Confirmed co-infection with influenza
8. Creatinine clearance < 45 mL/min or requiring acute renal replacement therapy
9. History or current diagnosis of ECG abnormalities indicating significant risk of safety for participants participating in the study such as:
 - Concomitant clinically significant cardiac arrhythmias, e.g. sustained ventricular tachycardia, and clinically significant second or third degree AV
 - History of familial long QT syndrome or known family history of Torsades de Pointe
 - QTcF > 480 msec (at screening and/or Day 1 at pre-dose) based on the local ECG data
 - Uncorrected electrolyte abnormalities, such as hypokalemia, hypomagnesemia and hypocalcemia
 - Use of agents known to prolong the QT interval within 5 half-lives before screening
10. Any other condition (e.g. known liver disease) which, in the opinion of the investigator, would put the safety of the participant at risk, impede compliance or hinder completion of the study
11. Pregnant or nursing (lactating) women

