8.3 Efficacy

8.3.1 COVID-19 Participant status

The following details on the participants' status will be collected in the at Baseline and hospital discharge at a minimum, in addition any change in status must be reported in the CRF:

- Hospitalization (including dates of admission and discharge* or ready for discharge)
- ICU stay (including dates of admission** and discharge***)
- Pre-morbid supplemental oxygen requirements and its volume if yes (start and stop dates, volume: L)
- Mechanical ventilation requirements (start and stop dates)
- Participant survival status (i.e. death)

[REDACTED]

* If a participant is unable to be discharged due to administrative reasons, then the date that the participant, in the opinion of the investigator, is ready to be discharged (i.e. ready for discharge as evidenced by normal body temperature and respiratory rate, and stable oxygen saturation on ambient air or $\leq 2L$ supplemental oxygen) should be reported in the hospitalization status for date of discharge.

** In the case that a participant cannot be admitted to the ICU, even if the participant's condition is severe enough in the opinion of the investigator (e.g. due to administrative reasons under the current circumstances), this is also considered under admission and date of ICU admission should be reported

***If a participant is unable to be discharged from ICU due to administrative reasons, then the date that the participant, in the opinion of the investigator, is ready to be discharged should be reported in the ICU status for date of discharge.

[REDACTED]

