1.2 Study objectives and endpoints

Study objectives and related endpoints are described in [Table 1-1](#) below.

Table 1-1 Objectives and related endpoints

Objectives	Endpoints

Primary Objective
 
 To demonstrate superiority of hydroxychloroquine or hydroxychloroquine plus azithromycin compared to placebo in achieving clinical response by Day 15 	
Endpoints for primary objective
 
The percentage of participants who achieve clinical response by Day 15 defined as:
 
 For participants with a pre-morbid oxygen requirement: 
 Discharge (or ready for discharge as evidenced by normal body temperature and respiratory rate, and stable oxygen saturation on ambient air or \leq 2L supplemental oxygen) OR Survival without need for mechanical ventilation For participants without a pre-morbid oxygen requirement: 
 Discharge (or ready for discharge); OR

Objectives	Endpoints
	
 Survival without need for mechanical ventilation or oxygen supplementation for the last 24 hours
Secondary Objectives	Endpoints for secondary objectives

 To demonstrate superiority of hydroxychloroquine or hydroxychloroquine plus azithromycin compared to placebo in achieving viral clearance by Day 15 	
 The percentage of participants with negative or below the lower limit of quantification LLOQ SARS-COV-2 based on polymerase chain reaction (PCR) test by Day 10

 To evaluate the time to discharge from the hospital in participants receiving hydroxychloroquine or hydroxychloroquine plus azithromycin relative to placebo 	
 Time to discharge (or ready for discharge)

 To evaluate the time to return to pre-morbid supplemental oxygen requirement in participants receiving hydroxychloroquine or hydroxychloroquine plus azithromycin relative to placebo 	
For the subset of patients who require supplemental oxygen at the time of randomization:
 
 Time to return to pre-morbid supplemental oxygen requirement

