2.2 Analysis sets

The **Randomized Analysis Set (RAS)** consists of all randomized participants regardless of receiving study treatment.

The **Full Analysis Set (FAS)** comprises all participant to whom study treatment has been assigned by randomization excluding mis-randomized participants. Mis-randomized participants are defined as cases where IRT contact is made by the Investigator/qualified site staff either prematurely or inappropriately prior to confirmation of the participant's final randomization eligibility and treatment is not administered to the participant. According to the intent to treat principle, participants will be analyzed according to the treatment they have been assigned to during the randomization procedure.

The **Safety Set (SAF)** includes all participants who received at least one dose of study treatment. Participants will be analyzed according to the study treatment received, where treatment received is defined as the randomized/assigned treatment if the participant took at least one dose of that treatment or the first treatment received if the randomized/assigned treatment was never received.

The analysis of the primary objective and all other efficacy variables will be performed on the FAS. The Safety Set will be used in the analysis of all safety variables.

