2.3.2 Background and demographic characteristics

Participant demographic and baseline characteristics will include:

- Age
- Age categories (≤ 65 , > 65 years)
- Sex
- Race
- Ethnicity
- Height
- Weight

[figure not shown]
- BMI

Background disease characteristics will include:

- Oxygen saturation at baseline ($\leq 94\%$; $> 94\%$)
- Requiring supplemental oxygen at baseline (No/Yes)
- Supplemental Oxygen Flow rate (L/min) (see also [section 2.4.2.3](#))
- Number of days from onset of symptoms to first dose of study drug
- Number days from hospital admission to first dose of study drug
- Chest imaging (x-ray or CT scan) status at baseline (Normal/Abnormal/not available)
- Pre-morbid oxygen requirement (No/Yes)
- 
- Tachypnea (i.e. respiratory rate > 24 bpm) at baseline (No/Yes)

Comorbidities will include:

- Number of comorbidities (0,1 >1) , where comorbidities include the following list of solicited terms: Cerebrovascular disease, Chronic heart disease, Hypertension, Asthma, COPD, Chronic kidney disease, Malignant neoplasm, Diabetes.

Demographic and other baseline data will be summarized descriptively by treatment group for all study participants in the FAS.

Categorical data will be presented as frequencies and percentages. For continuous data, mean, standard deviation, median, minimum, and maximum will be presented. For selected parameters, 25th and 75th percentiles will also be presented.

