5.5 Exclusion criteria of analysis sets

The RAS, FAS and SAF analysis set will be used in analysis. Rule for participant classification in analysis set is provided in [Table 5-2](#).

Table 5-2 Participant classification

Analysis Set	PD ID that cause participants to be excluded	Non-PD criteria that causes participants to be excluded
ENR	NA	Not having informed consent; Not having screening epoch disposition page
RAS FAS	NA	Not randomized Not in RAS;
SAF	NA	Mistakenly randomized and no double-blind study drug taken No double-blind study drug taken

5.6 Type of pulmonary/ventilatory support and component of the 9-point ordinal scale for clinical status

Table 5-3 Type of pulmonary/Ventilatory support

Type of support	Non invasive or invasive pulmonary support	Invasive pulmonary support
Low flow nasal oxygen	Yes	No
High flow nasal oxygen	Yes	No
Oxygen via face mask	Yes	No
Non-invasive ventilation	Yes	No
Mechanical ventilation	Yes	Yes
Intubation	Yes	Yes
Tracheostomy	Yes	Yes
ECMO	Yes	Yes

Table 5-4 9-point ordinal scale for clinical status

Score	Item
0	No clinical or virological evidence of infection
1	Ambulatory (defined as not in hospital or in hospital and ready for discharge): No limitation on activities
2	Ambulatory: Limitation of activities
3	Hospitalized Mild Disease: no oxygen therapy (defined as SpO2 \geq 94% on room air)
4	Hospitalized Mild Disease: oxygen by mask or nasal prongs
5	Hospitalized Severe Disease: non-invasive or high-flow oxygen
6	Hospitalized Severe Disease: Intubation and mechanical ventilation
7	Hospitalized Severe Disease: Ventilation plus additional organ support – pressors, Renal replacement therapy (RRT), Extracorporeal membrane oxygenation ECMO
8	Death

6 References

- Dmitrienko, A. and Koch, G.G., 2017. Analysis of clinical trials using SAS: a practical guide. SAS Institute.
- Firth, D, 1993. Bias reduction of maximum likelihood estimates. *Biometrika* **80**, 27-38.
- Heinze, G. and Schemper, M., 2002. A solution to the problem of separation in logistic regression. *Statistics in medicine*, 21(16), pp.2409-2419.

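### SAP 2.7.1 does not carry over the oxygen-at-randomization subset for return to pre-morbid oxygen, and it counts pre-morbid oxygen users as returned at any flow

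*SAP*

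**What the plan says.** Both objectives tables attach a population to this endpoint. SAP 1.2, Table 1-1, introduces it with "For the subset of patients who require supplemental oxygen at the time of randomization", and Protocol Table 2-1 has the same restriction.

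SAP 2.7.1 reports the number and percentage of participants returned by Day 15 and by Day 28. It names the FAS as the analysis set, does not mention the subset, and gives return as "defined as no need of mechanical ventilation in any participants and no need of supplemental oxygen in any participants without pre-morbid oxygen requirement". SAP 2.2 makes the FAS the general rule: "The analysis of the primary objective and all other efficacy variables will be performed on the FAS". The FAS definition there has no oxygen criterion. SAP section 4 declares no change from the protocol's analyses.

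Four other places matter:

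- **Eligibility.** Protocol 1.2 counts as moderate disease, and so admits, patients with SpO2 "> 94% on room air and requiring hospitalization".
- **Ventilation at entry.** Protocol 5.2, exclusion 5, bars anyone judged to need "admission to the intensive care unit (ICU) or mechanical ventilatory support (invasive or non-invasive) prior to the initiation of study drug".
- **Types of support.** SAP Table 5-3 gives "High flow nasal oxygen" its own row, apart from mechanical ventilation, and marks it as not invasive.
- **Oxygen data.** Protocol 8.3.1 collects "Pre-morbid supplemental oxygen requirements and its volume if yes (start and stop dates, volume: L". SAP 2.4.2.3 has oxygen flow in L/min solicited from screening through Day 15 and again at Day 40.

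**The concern.** An endpoint about returning to an earlier oxygen requirement makes sense only for someone whose requirement has risen, and it needs a comparison with the earlier level. SAP 2.7.1 falls short on both.

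First, it gives a programmer no instruction to apply the Table 1-1 subset. Participants who were never above their usual requirement could enter both numerator and denominator.

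Second, for participants with a pre-morbid requirement the rule contains no oxygen condition at all. Freedom from mechanical ventilation stands in for return to the usual flow, although the usual flow is collected. A home-oxygen user who now needs much more oxygen would be tabulated as back to normal.

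What is at stake is the meaning of a percentage in the abbreviated clinical study report. The label would claim a recovery that the rule does not establish.

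**Working it through.** **Step 1: apply the SAP 2.7.1 rule at entry.** No stated figure needs reproducing, so the check starts from the definition. An eligible participant does not need mechanical ventilation at entry (exclusion 5). The rule then reduces to: returned if there is a pre-morbid requirement, or if no supplemental oxygen is needed.

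| Pre-morbid requirement | Oxygen at randomization | In Table 1-1 subset | Meets 2.7.1 at entry |
|---|---|---|---|
| No | No | No | Yes |
| No | Yes | Yes | No |
| Yes | No | No | Yes |
| Yes | Yes, any flow | Yes | Yes |

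Three of the four states satisfy the rule before treatment. Restoring the subset removes rows 1 and 3. Row 4 remains, so the subset alone does not repair the definition.

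**Step 2: numbers available.** SAP 1.1 gives 20 randomized, including one mis-randomized. FAS = 20 − 1 = 19 if nobody else is excluded, and 19/3 = 6.3, so 6 to 7 per arm if allocation was even. The documents give no count of room-air participants or pre-morbid users, so everything below is assumed and shown as a range.

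**Step 3: room-air participants counted as met.** Let an arm have n participants, r of them on room air, with k returned among the m = n − r in the subset. Write s = r/n and p = k/m.

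Shift = (k + r)/n − k/m = s × (1 − p)

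| n | r | k/m (subset) | (k + r)/n (FAS) | Shift, points |
|---|---|---|---|---|
| 6 | 1 | 3/5 = 60.0% | 4/6 = 66.7% | +6.7 |
| 6 | 2 | 2/4 = 50.0% | 4/6 = 66.7% | +16.7 |
| 6 | 3 | 1/3 = 33.3% | 4/6 = 66.7% | +33.3 |
| 7 | 1 | 3/6 = 50.0% | 4/7 = 57.1% | +7.1 |
| 7 | 2 | 2/5 = 40.0% | 4/7 = 57.1% | +17.1 |

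The shift is 0 if r = 0 or p = 100%. It is also a maximum for given s and p, because every room-air participant is counted as met. If only a fraction q of them meet the rule when status is read, the shift is s × (q − p). With n = 6, r = 2, k = 2 and one of the two having deteriorated, the FAS rate is 3/6 = 50% and the shift is 0.

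**Step 4: effect on a contrast between arms.** If a share f of each arm is met at entry and stays so, each rate becomes f + (1 − f) × p and a difference shrinks by the factor 1 − f. For assumed subset rates of 60% and 40%:

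- f = 10%: 64% vs 46%, 18 points
- f = 30%: 72% vs 58%, 14 points
- f = 50%: 80% vs 70%, 10 points

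**Step 5: pre-morbid users inside the subset.** Each one counted as returned while above their own usual flow adds 1/m:

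- m = 7: 14.3 points
- m = 6: 16.7 points
- m = 5: 20.0 points
- m = 4: 25.0 points
- m = 3: 33.3 points

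If there are no such participants, nothing is added.

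**The case against.** **The FAS may mean the FAS within the subset.** Table 1-1 of the same SAP keeps the restriction, SAP 2.2 uses the FAS as the default for every efficacy variable, and the word return itself implies a raised requirement. This reading is tenable. On it, the first part is only missing wording, and Steps 3 and 4 do not arise. It does nothing for pre-morbid users within the subset.

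**Meeting the rule at entry is an inference.** SAP 2.7.1 speaks of return by Day 15 and by Day 28 and does not say that baseline status counts. If status is read at Day 15, a room-air participant who has deteriorated fails, as does a pre-morbid user who has been ventilated. The inference also assumes that exclusion 5 was applied without error. This limits the size in Step 3. It does not help with a pre-morbid user who is unventilated but on raised flow at Day 15, who is still counted.

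**Derivations may be hidden.** SAP 2.5.1 ends in a redacted block, which could define need of mechanical ventilation more broadly. That leaves some doubt about the high-flow example. But SAP 2.7.1 gives its own complete, unredacted definition, and the lack of a flow comparison does not depend on that block.

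**The rule may be deliberate.** The primary endpoint uses the same split by pre-morbid requirement, and the SAP says its analyses were simplified after the halt. That may explain the wording. It does not turn absence of ventilation into a return to the pre-morbid oxygen level.

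**Conclusion.** The concern holds; it is minor. The mismatch with Table 1-1 is plain on the text: a wording gap on the generous reading of FAS, and an undeclared change of population on the literal one. The missing oxygen condition for pre-morbid users is a fault on either reading, and only that part necessarily changes what the percentage means.

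The size cannot be fixed from the documents. With arms of 6 to 7, even allocation and the assumed counts above, the percentage in an arm could be overstated by about 7 to 33 points through room-air participants, on the literal reading and with all of them counted as met. Each misclassified pre-morbid user adds about 14 to 33 points. Both can be zero. No hypothesis test, confidence interval or power statement is affected.

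**What to change.** In SAP 2.7.1:

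1. Restrict the summary to FAS participants who require supplemental oxygen at randomization, as Table 1-1 says.
2. For pre-morbid users in that subset, base return on the recorded flow against the recorded pre-morbid volume where both exist, after confirming that the volume in L is a flow in L/min.
3. Where both do not exist, report pre-morbid users separately and state that return cannot be assessed.

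The first change is a sentence and a filter. SAP 2.3.2 already tabulates "Requiring supplemental oxygen at baseline (No/Yes", but SAP 2.1.1.3 takes baseline as the last assessment before study Day 1, whereas randomization is on Day 1 and oxygen is solicited at both screening and Day 1. The filter should use status at randomization, and any disagreement with the baseline variable should be resolved. Separate reporting needs no new data, since pre-morbid requirement is tabulated in the same section. The flow comparison needs some programming.

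The price is a smaller denominator and incomplete flow data. Flow is not solicited at Day 28, and Protocol 8.5.2 allows the Day 15 visit to be a phone call, so for some participants item 3 will be all that can be done.
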